- d) Once determined to be eligible, the paramedics will open the cooler, remove the two cassettes from the sealed bag, and open both cassettes to determine their contents. Once the cassettes are opened, the patient will be randomized to one of the 2 arms. If the cooler contains two units of AB-FP24, the patient is randomized to the experimental group. If the cooler contains non-infusable frozen water, the patient is randomized to the control group. All ambulances will be equipped with a Plasmatherm and a cooler storage box containing either plasma or noninfusable

frozen water. Before transfusing any fluids (likely immediately before drawing blood so as not to hinder patient care), paramedics will apply the noninvasive device for recording continuous waveform data. This device will remain on the patient for 24 hours and will begin obtaining critical physiological information as soon as the monitoring begins. Since this is an observational component of the study, there will be no changes made to the patient's care during this portion. Waveform data will not be used in the provision of subsequent care.

- e) If the patient is randomized to the control arm, the patient will be given intravenous normal saline as the initial resuscitation fluid with 2 large bore IVs based on the current ATLS guidelines. Subsequent care will proceed per institutional, ATLS guided resuscitation with acute pRBC administration determined by hemodynamic response and additional blood component administration guided by rTEG and coagulation panel assessment in conjunction with clinical scenario. The Massive Transfusion Protocol may be initiated using the ABC score⁶⁹ and heuristic evaluation of uncontrolled hemorrhage of the attending surgeon (See Appendix 1 for DHMC Massive Transfusion Protocol)

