- f) If the patient is randomized to experimental arm, 2 units of frozen AB-FP24 will be thawed in the Plasmatherm thawing device according to the operator manual as approved by the FDA (see Plasmatherm- section IV.L.2) in the ambulance and infusion will commence as soon as the AB-FP24 is ready, and will continue during transport to the ED. If the AB-FP24 is not ready, but IV access is acquired, normal saline will be infused and the volume recorded. Once the AB-FP24 is ready, the normal saline infusion will be stopped and the AB-FP24 will be started. If the patient has 2 lines, both lines will be used for AB-FP24. If only 1 IV is available, one unit of AB-FP24 will be infused until it either is completed or another line is available for infusion. The experimental group will receive at least the standard of a resuscitation fluid, regardless if the AB-FP24 is ready for infusion. After infusion of 2 units of AB-FP24 is completed, subsequent care will proceed per institutional, ATLS guided resuscitation with acute pRBC administration determined by hemodynamic response and additional blood component administration guided by rTEG and coagulation panel assessment in conjunction with clinical scenario. The Massive Transfusion Protocol may be initiated using the ABC score⁷² and heuristic evaluation of uncontrolled hemorrhage of the attending surgeon, similar to the standard arm. (See Appendix 1 for DHMC Massive Transfusion Protocol)
- g) Both groups will be managed based on the critical care guidelines for trauma patients as published in the Journal of Trauma, which is the routine hospital care for trauma patients at DHMC.⁷⁰⁻⁷⁸ These are Standard Operating Procedures for critical care management specifically developed and peer-reviewed during our NIH sponsored Glue Grant studies

- h) In the unlikely event multiple patients are enrolled in this study, all patients will be maintained as study patients despite the fact that there will be logistic barriers to obtaining a complete laboratory assessment. The rationale for this policy is the primary endpoint of this study is mortality; whereas, laboratory assessments are secondary endpoints.
- There will be no ceiling dose for the total amount of intravenous fluids that will be administered in the field. Based on our experience, no more than 700cc of normal saline on average is infused prior arrival to the ED.

[figure not shown]
C. Data Collection and Storage

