Mixed linear modeling with SAS Proc Mixed allows for incomplete data, thus all observed points will be used in the analysis. Missing data in temporal trends will be dealt with differently depending on the reason for missing. If MAR (loss to followup, withdrawn from study), multiple imputation methods will be used, as recommended by the Panel on Handling Missing Data in Clinical Trials. However, as described in previous sections, a major reason for missing data in these cases is early death, resulting in data MNAR, for which we will use the same approach to deal with the missing data as described for the secondary endpoints.

A similar analysis will be carried out for temporal trends in Proteomic Profile, Actin and Neutrophil Elastase inhibitors.

5. Blood components transfusion in the first 12 hours postinjury

a. Packed Red Blood Cells (RBC) volume

1. **Hypothesis:** The volume of RBC transfused in the first 12 hours postinjury will be larger among control patients compared to the experimental group patients.

b. Plasma volume

- **1. Hypothesis:** The volume of plasma transfused in the first 12 hours postinjury will be larger among control patients compared to the experimental group patients.
- 2. Statistical test for a.1 and b.2: These variables are usually non-normally distributed, thus the Wilcoxon non-parametric test will be used to compare the two groups and median/interquartile range will be used to express data central tendency and dispersion. If adjustment for covariates is needed, we will follow the procedure described for continuous, not normally distributed variables. Overall experiment error will be adjusted for the number of blood transfusion parameters being analyzed using the Bonferroni method.
- c. **Time to first RBC:** This is a variable of high importance for DOD, which leads to direct application in war theater trauma.

- **1. Hypothesis:** Time to the first RBC will be longer among patients in the experimental group compared to control patients.

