the patient to the hospital as soon as possible. Paramedics cannot assess competency of family members in this time-sensitive setting; thus family members that are not in shock or severely injured will be assumed to be competent.

- **8.** It will be assumed that patients will not be competent to give an assent since by nature of the eligibility criteria, the patient will be in severe shock.
- 9. If the patient will not be transported to Denver Health, he/she will not be enrolled. If the patient is enrolled, but due to unforeseen circumstances (such as impending airway), must be transported to a nearby facility that is not Denver Health, then the patient will be unenrolled. If possible, every effort will be made to contact the family and follow the patient for any adverse effects. The consent form will be used to verify that the patient (or family) was informed.

K. Procedures involving plasma

- 1. Procedure for thawing frozen AB-FP24: AB-FP24 will be thawed in the Plasmatherm (see section IV.L.2) and in accordance to the instructions accompanying the product and as approved by the FDA.
- **Plasma is thawed but not transfused:** If the AB-FP24 is thawed but not transfused for unforeseen reasons, such as discovery of Jehovah's Witnesses, then the unit(s) will be discarded or used for research purposes. It will not be transfused into humans.
- 2. Procedure for Issuing 2 units of AB-FP24: Bonfils Blood Center will be providing the AB plasma for the study.. This is modified from the DHMC policy for Blood Transfusions to be applicable to this study.
 - a. AB-FP24 will be administered through the standard Y-set with blood transfusion filter (170-260 micron).
 - b. Vital signs are required before the transfusion of all components and again after 15 minutes and at the completion of the transfusion. Transfusion rate will be compatible with the patient's condition. The patient will be monitored closely during the entire transfusion. The documented start and stop times are directly related to the actual transfusion of the component. Paramedics will document vital signs and start times in the field. Study coordinators will assume responsibility of additional vital signs and stopping time of the AB-FP24.
 - c. The patient medical record shall include the following:
 - **1.** Name of the components transfused
 - 2. Donor identification number of components
 - 3. Date and time of transfusion (Start and Stop time)
 - **4.** Pre and post transfusion vital signs

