- a. Plasmatherm functions similarly to the typical water bath, however, the water does not contact the plasma, reducing the potential for contamination in the event of back breakage. If a bag breaks, Plasmatherm is easier to clean up than a typical water bath.

- b. Monthly, the Plasmatherm will be inspected for damage and cleaned. If there is any concern regarding the use of the Plasmatherm, the Pl will be notified. Before each shift, the display will be tested
- **3.** CipherOx M1 by Flashback Technologies is a non-FDA approved device consisting of an FDA-approved Nonin OEM III pulse-oximeter integrated with an ARM III processors, memory, a mini-USB port for charging and data off-load, as well as a high-resolution screen for indoor and outdoor use. The device collects non-invasive waveform data from acutely injured, potentially bleeding trauma patients. The device displays the date/time and an image of a finger with a sensor that is displayed in "green" if the data collection is "good." The providers are blinded to all physiological data collection by the device.

M. Special Consent Issues

- 1. We have requested an exception from informed consent for emergency research under 21 CFR §50.24 as the patients selected for enrollment in this clinical study will be unable to provide prospective informed consent due to the extent of their injuries and their immediate need for resuscitation from life-threatening hemorrhagic shock. These patients are often unable to give consent upon arrival, and this study cannot be carried out without an exception from informed consent.
 - a. The therapeutic window dedicated to obtaining prospective informed consent from the patient or a legally authorized representative is very brief. On average, line-placement has been accomplished by experienced field care personnel in approximately one minute, and therefore, the process of patient assessment, scene care, randomization, enrollment, thawing of plasma, and the start of AB plasma infusion can be expected to occur in less than 8 min. The opportunity to obtain prospective informed consent from the patient or a legally authorized representative or to provide an opportunity for a family member to object to the subject's imminent enrollment in the study may not be possible prior to the commencement of study procedures.

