The contract with the Department of Defense is specific to the evaluation of the use of plasma in the field. As described above, the majority of potentially survivable injuries are due to hemorrhage. If administering plasma earlier in the field decreases hemorrhage from acute coagulopathy of trauma, injured members of the armed forces may have more time to reach a facility to be better stabilized and resuscitated. Although some institutions have adopted the principle of early plasma administration in the management of severe trauma and the acute coagulopathy of trauma, there are no prospective studies measuring the benefit and risks of administering plasma early.

Although this is a greater than minimal risk study, subjects are likely to receive direct benefit from this clinical trial from closer evaluation and testing of coagulation status. Based on the previous retrospective studies and preclinical studies described in the Section II.A. (Background) and Section III.A. (Preliminary studies) as well as our current understanding of administering plasma earlier and more frequently in the resuscitation of patients in severe hemorrhagic shock, patients receiving early plasma are likely to directly benefit from this study.

This study will be carried out in accordance with 21 CFR §50.24 Exception from Informed Consent for Emergency Research.

N. Description of Risks, Benefits and Justification

 Risk of blood transfusion: These risks apply to any patient that receives blood products regardless of group assignment. Both the standard and experimental groups are likely to receive blood products during the resuscitation period, but

the study group will receive at a minimum 2 units of AB plasma. In this study, all plasma used as an initial resuscitation fluid will be AB and hence universally infusible without the requirement for patient blood typing. This is the usual type of fresh frozen plasma used in acute trauma setting prior to obtaining type and cross

Table 3: Risk of Disease from Blood Product Transfusion				
Transmitted Blood Product Disease	US Transmission Risk/Unit Transfused			
Hepatitis A Virus (HAV)	1:8,300,000			
Hepatitis B Virus (HBV)	1:282,000			
Hepatitis C Virus (HCV)	1:1,149,000			
Human Immunodeficiency Virus (HIV-1, -2)	1:1,467,000			
Malaria	1:4,000,000			
Human T-cell lymphotrophicvirus (HTLV-I, -II)	1:2,990,000			

match (see appendix 9 for adult transfusion guidelines). Risks of blood

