transfusion include febrile non-hemolytic transfusion reaction (1.1% to 2.5%), hemolytic transfusion reactions (1:1,250,000), transmission of blood borne pathogens (See Table 2), transfusion-related lung injury (TRALI) (8.1 per 100,000), transfusion associated circulatory overload (TACO) (2-3 per 100).¹¹² A blood transfusion may also result in a reaction that includes fever, chills, or hives. Although uncommon, the patient may experience this type of reaction as the result of receiving the incorrect type of blood. By using AB type of plasma, this risk is minimized. This risk is minimized in the blood bank by a questionnaire to exclude donors who are at risk of having a blood borne pathogen as regulated by the FDA under 21CFR 640 subpart G. The donated blood is also tested in the laboratory for infectious diseases.

A blood transfusion may increase the likelihood of developing an infection while the patient is in the hospital, may exaggerate how the patient's body responds to injury, and may increase the patient's risk of internal organ failure after his/her injury.

Excessive transfusions place patients at higher risk of hypervolemia, and pulmonary edema, but this risk also exists for patients who receive excessive intravenous fluids. The risk of 2 units of AB-FP24 as initial resuscitation leading to cardiac failure, hypervolemia and pulmonary edema is low as it is a smaller volume (500ml) than the standard 2 liters of crystalloid intravenous fluid. These risks exist with transfusions of any blood products

- Risk of Inadvertent Release of Protected Health Information (PHI): This risk is minimized by using a unique patient identifier and role based security for the database. All hard copies will be kept locked in the research office or be destroyed.
- **3.** Venipuncture risk: In most cases blood will be drawn from an intravenous line (I.V.) already placed as part of the patient's standard medical care. In the event the patient does not have an I.V., blood will be drawn using a method known as venipuncture. This procedure consists of placing a small needle in a vein in the patient's arm to withdraw blood. Risks associated with drawing blood from the patient's arm include pain, bruising, lightheadedness, and rarely infection.

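### As worded, the exploratory 12-hour plasma volume counts the two study units given only to the experimental arm, so allocation largely determines the Wilcoxon result

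*Combined protocol and SAP*

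**What the plan says.** All places are in the combined protocol and SAP.

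- **Endpoint and hypothesis (IV.G.5.b):** "The volume of plasma transfused in the first 12 hours postinjury will be larger among control patients" than among experimental patients. The count is not limited to hospital plasma or to plasma after the field dose.
- **Test (IV.G.5.b):** Wilcoxon, with Bonferroni adjustment over the transfusion parameters.
- **Experimental arm (IV.B.1.f):** "2 units of frozen AB-FP24 will be thawed in the Plasmatherm thawing device" in the ambulance, and infusion starts when they are ready. IV.M.1.a says that "the start of AB plasma infusion can be expected to occur in less than 8 min". IV.N.1 says that "the study group will receive at a minimum 2 units of AB plasma" and gives the volume of the two units as 500 ml.
- **Control arm (IV.B.1.e):** "the patient will be given intravenous normal saline as the initial resuscitation fluid". Blood components follow only if later care calls for them.
- **Vocabulary and records (IV.K):** the study product is described with the endpoint's own verb, as in "If the AB-FP24 is thawed but not transfused for unforeseen reasons". The medical record must hold component name, donor number, start and stop times and volume.
- **Use of the result (IV.I.1.c and IV.I.2.a):** significant exploratory results can count toward calling the therapy promising, and exploratory analyses go to the DSMB.

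**The concern.** The hypothesis is about need: plasma given early should mean less plasma later. The quantity defined is everything transfused in 12 hours, and two units of that are given to one arm by assignment. Many controls may receive no plasma at all, so a typical experimental patient can outrank a typical control whatever early plasma does to later bleeding.

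Three things follow. A difference caused by the design could be read as greater need in the experimental arm. A real fall in later plasma could be hidden. And a test with little chance of supporting its own hypothesis still takes a share of the Bonferroni allowance from the red-cell volume test.

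**Working it through.** The plan gives no effect size, power or sample size for this endpoint, so there is no figure of its own to reproduce.

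**Inputs from the documents**
- Analysed patients: 112 per arm with 12% attrition (IV.E addendum), so 112 × 0.88 = 98.6, about 99.
- Alpha: 0.05 / 2 = 0.025, taking red-cell and plasma volume as the two parameters. Two-sided, assuming that the footnote to the primary hypothesis applies here too.
- Share with no plasma: the same addendum reports that 55% of group A and 61% of group B required transfusions, against 64% anticipated. Group A's mortality (12%) and INR (1.32) match the control figures used there, so I infer that A is control. That gives 1 − 0.55 = 45% observed and 1 − 0.64 = 36% anticipated with none.

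**Assumptions, because the documents are silent**
- 60% with none is added as a third value, since some transfused patients may get red cells only.
- Hospital plasma among recipients is geometric with mean 3 or 6 units.
- Both study units reach 100%, 80% or 60% of experimental patients.
- Analysis is by assigned arm.

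**Study units counted.** Hospital plasma has the same distribution in both arms. Volume is H for controls and H + 2 for experimental patients who received the study units. There were 1,000 runs per cell, so the Monte Carlo standard error is at most √(0.25/1000) = 1.6 points. The last two columns let study units replace hospital units one for one, so volume is max(H − 2, 0) + 2.

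Percentage of runs declaring the experimental arm larger:

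| None | Mean units | 100% delivered | 80% | 60% | Replacement, 100% | Replacement, 60% |
|---|---|---|---|---|---|---|
| 36% | 3 | 100 | 100 | 98 | 99.5 | 80 |
| 36% | 6 | 99 | 92 | 69 | 83 | 37 |
| 45% | 3 | 100 | 100 | 99 | 100 | 92 |
| 45% | 6 | 99.8 | 97 | 79 | 97 | 60 |
| 60% | 3 | 100 | 100 | 100 | 100 | 99 |
| 60% | 6 | 100 | 100 | 96 | 100 | 93 |

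The hypothesised direction was declared in none of these cells.

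**A real benefit, study units counted.** Hospital plasma is halved in the experimental arm, with means of 4 or 6 units and 80-100% delivery. The test still declares the experimental arm larger in 72-100% of runs (45% with none) or 38-98% (36% with none).

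**Limiting case.** Every experimental patient has exactly 2 units, and every control who gets any plasma has more than 2.
- 45 of 99 controls at zero: U = 99 × 45 = 4,455 against a null mean of 99 × 99 / 2 = 4,900.5. P(experimental > control) = 45/99 = 0.45 and p = 0.23, so the hypothesis fails even here.
- 36 of 99 at zero: U = 99 × 36 = 3,564 and p = 0.0004 in the hypothesised direction.

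**Study units excluded (mean 6 units, 99 per arm).**
- No effect and no replacement: total rejection 2.0-2.6%, the nominal size.
- One-for-one replacement only: controls larger in 61%, 48% and 31% of runs with 36%, 45% and 60% having none.
- True halving of hospital plasma: 60%, 42% and 20%.

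The excluded version therefore cannot tell replacement from a real fall in need.

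**The case against.** **Total plasma is a legitimate question.** Study aim 3 asks about overall blood product transfusion, and study units are part of consumption. This stands. Total plasma should be compared and reported, and a claim of lower overall use can rest only on it.

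**Testing only non-study plasma tilts the other way.** This also stands. Later components are guided by rTEG, coagulation panel and clinical scenario (IV.B.1.f), so replacement is plausible. Under a different assumed distribution (112 per arm, 1 + Poisson(4) units in 30-60% of patients, full delivery), replacement alone gives controls larger in 13-75% of runs. A reader might infer that dropping the study units settles the matter. It does not: the nominal 2.0-2.6% holds only if field plasma never displaces later plasma.

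**Exclusion may be intended.** With 55% and 61% reported as requiring transfusions, neither interim group is near 100%, so that count left out study plasma or meant red cells. IV.C.1.a lists resuscitation fluids separately from blood products, and the hypothesised direction is natural only without the study units. These are hints about intent. None defines this endpoint, and the wording of IV.G.5.b includes the units.

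**The consequence is small.** The endpoint is exploratory, the distortion in the current wording runs against the experimental arm, and the two-unit dose is known to all. That limits the weight of the point. It does not make the result interpretable.

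**Conclusion.** The point holds with limits. IV.G.5.b as worded counts the study units, and for realistic inputs allocation largely determines the test. With no effect on hospital plasma, the experimental arm is declared larger in about 99-100% of trials at full delivery and in roughly 70% to almost 100% at 60% delivery. The hypothesised direction is essentially never declared.

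These figures rest on assumed hospital-plasma distributions, an assumed delivery rate, transfusion shares that are not specific to plasma, and an inferred control group.

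A reader might infer that the hypothesis cannot be tested at all, or that a wrong-direction result is certain. The documents do not support either. With 36% of controls at zero, the limiting case reaches p = 0.0004 in the hypothesised direction. Certainty would also need every patient to receive both units, whereas IV.K provides for thawed plasma that is not transfused and IV.D.3 plans an analysis by plasma dose received in the field.

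The primary endpoint and the red-cell endpoint definitions are not touched. This is a minor point of endpoint definition, worth settling because IV.I.1.c gives significant exploratory results a role in judging promise.

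**What to change.** Amend IV.G.5.b to say:

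1. The hypothesis of lower later plasma need is assessed on plasma transfused within 12 hours, excluding the study AB-FP24 units.
2. The between-arm comparison of total plasma, including those units, is reported beside it.
3. The first is shifted toward more in controls if study units merely replace hospital plasma. The second is shifted toward more in the experimental arm by allocation.
4. A claim of reduced overall plasma use requires the total. Neither result alone supports calling the therapy promising under IV.I.1.

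The cost is wording and one extra reported comparison. If both plasma measures are tested along with red-cell volume, the Bonferroni level becomes 0.05 / 3 = 0.0167 instead of 0.025. No new data are needed, because IV.K.2.c already requires component, donor number, times and volume to be recorded.
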